#### 11.3.1.2. Definition of Serious Adverse Event

The ICH topic E2A on Clinical Safety Data Management, Definitions and Standards for Expedited Reporting defines an SAE as any untoward medical occurrence that at any dose:

- Results in death
- Is life threatening  
NOTE: The term "life threatening" in the definition of "serious" refers to an event in which the patient was at risk of death at the time of the event; it does not refer to an event which hypothetically might have caused death if it were more severe.
- Requires inpatient hospitalization or prolongation of existing hospitalization
- Results in persistent or significant disability/incapacity
- Is a congenital anomaly/birth defect

Medical and scientific judgment should be exercised in deciding whether expedited reporting (see Section 11.3.1.9) is appropriate in other situations, such as important medical events that may not be immediately life threatening or result in death or hospitalization but may jeopardize the patient or may require intervention to prevent one of the other outcomes listed in the definition above. These should also usually be considered serious. Examples of such events are intensive treatment in an emergency room or at home for allergic bronchospasm; blood dyscrasias or convulsions that do not result in hospitalization; or development of drug dependency or drug abuse.

To ensure there is no confusion or misunderstanding of the difference between the terms “serious” and “severe”, the following note of clarification is provided:

The term “severe” is often used to describe the intensity (severity) of a specific event (as in mild, moderate, or severe myocardial infarction); the event itself, however, may be of relatively minor medical significance (such as severe headache). This is not the same as “serious,” which is based on patient/event outcome or action criteria usually associated with events that pose a threat to a patient’s life or functioning. Seriousness (not severity) serves as a guide for defining regulatory reporting obligations.

#### 11.3.1.3. Assessment of the Severity of Adverse Events

The severity (toxicity grade) of AEs will be graded according to the NCI CTCAE, Version 4.03 (see [Appendix 1](#)).

#### 11.3.1.4. Assessment of the Relationship of Adverse Events to Study Drug

The investigator will determine the assessment of the causal relationship of the AE to the study drug. The following terms for assessment of the causality to study drug or study procedures are to be used:

- **Unrelated:** There is not a temporal relationship to study drug administration (eg, too early, too late, or study drug not taken), or there is a reasonable causal relationship between another drug, concurrent disease, or circumstance and the AE.
- **Unlikely Related:** There is a temporal relationship to study drug administration, but there is not a reasonable causal relationship between the study drug and the AE (ie, the AE is doubtfully related to study drug).
- **Possibly Related:** There is a reasonable causal relationship between the study drug and the AE. Information related to withdrawal of study drug is lacking or unclear.
- **Probably Related:** There is a reasonable causal relationship between the study drug and the AE. The event responds to withdrawal of study drug. Re-challenge is not required.
- **Definitely Related:** There is a reasonable causal relationship between the study drug and the AE. The event responds to withdrawal of study drug, and recurs with re-challenge, when clinically feasible.

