#### 6.1.1.1. Definition of Dose-Limiting Toxicities (Applicable to Cycle 1 of the Phase 1b Dose-Finding Portion of Part 1)

Dose-limiting toxicities are drug-related toxicities defined as follows:

- Absolute neutrophil count (ANC)  $< 0.5 \times 10^9/L$  lasting for  $\geq 7$  days
- $\geq$  Grade 3 neutropenic infection/febrile neutropenia
- Grade 4 thrombocytopenia or  $\geq$  Grade 3 thrombocytopenia with bleeding
- Unable to start next cycle of chemotherapy due to lack of recovery to an ANC  $\geq 1.5 \times 10^9/L$  and platelet count  $\geq 100 \times 10^9/L$
- $\geq$  Grade 3 nonhematologic toxicity (nausea, vomiting, and diarrhea failing maximal medical management; fatigue lasting for  $> 72$  hours)

Toxicities not clearly related to etoposide/carboplatin (E/P) therapy will also be considered for the purposes of determining DLTs.

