- If there is > 1 DLT in the first cohort of 6 patients enrolled in the Phase 1b dose-finding portion of Part 1 and the available G1T28 PK parameters from these 6 patients are as predicted (Section 6.1.1.2), the dose of G1T28 should be decreased to 160 mg/m^2 and an additional 6 patients should be enrolled at the modified G1T28 dose in combination with E/P therapy. For assessment of data from the second cohort enrolled in the Phase 1b dose-finding portion of Part 1, please see the decision tree in [Figure 6-2](#).
- If there is > 1 DLT following a G1T28 dose of 160 mg/m^2 in combination with E/P therapy in the second cohort of patients and if available, PK parameters are as predicted (Section 6.1.1.2), an additional cohort of 6 patients will be enrolled at a further decreased G1T28 dose of 130 mg/m^2 in combination with E/P therapy. For assessment of data from the third cohort enrolled in the Phase 1b dose-finding portion of Part 1, please see the decision tree in [Figure 6-2](#).
- If there is > 1 DLT following the second dose reduction of G1T28 and if available, PK parameters from the third cohort are as predicted (Section 6.1.1.2), no further dose modifications will be made and the study will be terminated.
- At any time, if ≥ 2 DLTs are observed in any given cohort, further enrollment into that cohort will be stopped until the SMC can review the available data and make dose and cohort recommendations.

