An unexpected AE is any AE that is not identified in nature, severity, or frequency in the current Investigator Brochure or product information.

- An unexpected ADR is an adverse reaction, the nature or severity of which is not consistent with the applicable product information (eg, IB for an unapproved investigational medicinal product). All noxious and unintended responses to a medicinal

product related to any dose should be considered ADRs. The phrase “responses to a medicinal product” means that a causal relationship between a medicinal product and an AE is at least a reasonable possibility, ie, the relationship cannot be ruled out. All serious and unexpected ADRs will have expedited reporting to the regulatory agencies following the International Conference on Harmonisation (ICH) requirements

It is the responsibility of the investigator to document all AEs that occur during the study and every effort should be made to remain alert to possible AEs. Patients should be encouraged to report AEs spontaneously or in response to general, nondirected questioning. Adverse events should be reported on the appropriate page of the eCRF.

In the event of an AE, the primary concern is the safety of the patient. If necessary, appropriate medical intervention should be provided, and the investigational drug discontinued.

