5.1.1.11. Time to First Major Adverse Hematologic Event (MAHE)

As a composite measure of trilaciclib effect, MAHE is based on a combination of individual components specified in [Table 5](#), which also include details about the derivation or data source for each component. Time to first occurrence of a MAHE event is defined as the first time to observe an interested event among all the component, starting from the first dose date of study drug administration.

Therefore, for a patient with presence of MAHE events, time (months) to first occurrence of a MAHE event will be the minimum among the 7 potentially derived duration (i.e. calculated as (date of first occurrence of a MAHE component event – first dose date of study drug administration + 1)/30).

Table 5 Component of MAHE and the Suggested Data Source/Derivation Algorithm

Seq #	Component of MAHE	Criteria to identify the date of first occurrence of event
1	Hospitalization for a hematologic event (e.g. febrile neutropenia, thrombocytopenia, hemoptysis, etc)	Each hospitalization for a hematologic event (e.g. febrile neutropenia, thrombocytopenia, hemoptysis, etc.) is captured in AE data of electronic database. The event terms are coded using the MedDRA Version 20.1. Some suggested PTs are listed in Table 6 . These PTs will be broken into those that are always counted if they result in hospitalization, and those that will be subject to a case by case medical review to determine if the hospitalization is a hematologic event. All review will be finalized prior to study unblinding.
2	Febrile neutropenia	Detailed in Section 5.1.1.1
3	Death related to treatment (including backbone chemotherapy and trilaciclib)	An AE with its outcome being death, if its relationship to any of the study drugs (etoposide, carboplatin, or trilaciclib) is “Possibly Related”, “Probably Related”, or “Definitely Related”.
4	Dose delay/reduction due to ANC or platelet counts	Detailed in Section 5.1.3.4
5	Duration of Grade 4 neutropenia > 5 days	Detailed in Section 5.1.1.8 . If the duration (days) within a cycle is censored, even the duration of Grade 4 neutropenia

Seq #	Component of MAHE	Criteria to identify the date of first occurrence of event
		is \leq 5 days, the event will still be considered to meet the criteria. 5.1.1.2
6	RBC transfusion (actual or eligible)	Detailed in Section 5.1.1.2
7	Platelet transfusion (actual or eligible)	Detailed in Section 5.1.1.3

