6.2.8.1. Adverse Events

Number and incidences rates of AEs will be summarized by SOC and/or PT for the following categories of TEAEs: all AEs, SAEs, AEs leading to death, and AEs leading to study drug discontinuation or study withdrawal. Patients with more than one occurrence of the same SOC (PT) will be counted only once within the SOC (PT) categorization.

AEs will also be summarized similarly by CTCAE grade and relationship to study drug (trilaciclib, carboplatin, and etoposide), and the drug related AE summary will be appropriately evaluated by each drug. Should a patient experience more than one occurrence of the same SOC (PT), the patient's worst occurrence (worst grade/most related causality) will be retained in the tabulation.

All AEs, including AEs that started prior to the study medication, will be presented in patient listings. In addition, separate listings of all SAEs, AEs leading to death, drug-related AEs, and AEs leading to study drug discontinuation or study withdrawal will be provided.

For the AEs related to infusion and related to hematologic toxicity, the criteria for identifying them are described in [Section 5.2.1](#). A summary table showing incidence of AEs related to infusion and related to hematologic toxicity will be presented along with its supportive data listing.

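### The causality terms overlap: a reasonable alternative cause is enough for Unrelated even when the study drug is also a reasonable cause, so related-AE and related-SAE counts may be too low by an unknown amount

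*Protocol*

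**What the plan says.** Protocol Section 11.3.1.4 offers the investigator five causality terms. *Unrelated* has two limbs, and either one is enough. The first is the absence of a temporal link. The second is "or there is a reasonable causal relationship between another drug, concurrent disease, or circumstance and the AE". *Possibly Related* reads: "There is a reasonable causal relationship between the study drug and the AE. Information related to withdrawal of study drug is lacking or unclear". It does not require other causes to be absent, and nothing ranks the two terms when an event fits both.

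Section 11.3.1.1 describes an adverse drug reaction as one where "a causal relationship between a medicinal product and an AE is at least a reasonable possibility, ie, the relationship cannot be ruled out".

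The ratings are used in these places:

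- Protocol Section 13.5.1 lists related AEs and related SAEs as safety endpoints.
- SAP Section 6.2.8.1 summarises AEs by "relationship to study drug (trilaciclib, carboplatin, and etoposide").
- SAP Section 5.1.1.11, Table 5, counts a fatal AE as treatment-related "if its relationship to any of the study drugs (etoposide, carboplatin, or trilaciclib) is" Possibly, Probably or Definitely Related.
- Protocol Section 6.1.1.1 opens with "Dose-limiting toxicities are drug-related toxicities defined as follows" and closes with "Toxicities not clearly related to etoposide/carboplatin (E/P) therapy will also be considered for the purposes of determining DLTs". It does not cite the causality scale.

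**The concern.** A causality scale should give one answer per event. Here the term that excludes the drug most firmly can be reached without judging the drug at all. *Unlikely Related*, the weaker exclusion, does require the link to study drug to be judged not reasonable. *Unrelated* does not.

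This matters more here than in most trials. The expected harms of G1T28 and of chemotherapy coincide. Protocol Section 4.1 cites neutropenia in 47% to 92% of patients on a platinum agent with etoposide. Section 4.3.4 gives reduced hematopoiesis in all lineages as the chief animal toxicity of G1T28. Section 8.4.4.1 names worse myelosuppression as a possible result of insufficient arrest. For the hazard that the protocol itself anticipates, another drug is nearly always a reasonable cause.

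At stake are the related-AE and related-SAE summaries. One reporting route is also affected: under Section 11.3.1.9, an SAE after the 30-day window must be reported if it is thought to be related.

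**Working it through.** No sample size, power figure or event count in the plan depends on this definition, so there is no plan figure to reproduce. The check is one of logic, followed by a conditional illustration.

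**Step 1. Which terms does an event meet?** Take the Section 11.3.1.4 wording as written.

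| Temporal link | Study drug a reasonable cause | Other reasonable cause | Terms met |
|---|---|---|---|
| No | – | – | Unrelated |
| Yes | No | No | Unlikely Related |
| Yes | No | Yes | Unrelated and Unlikely Related |
| Yes | Yes | No | Possibly Related or stronger |
| Yes | Yes | Yes | Unrelated **and** Possibly Related or stronger |

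The third row also overlaps, but both its terms lie outside the ratings that SAP Table 5 counts as related. The last row straddles that line.

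**Step 2. Compare with Section 11.3.1.1.** In the last row the relationship cannot be ruled out, so the event is a reaction there, yet it may be rated *Unrelated* in Section 11.3.1.4. Measured against Section 11.3.1.1, each use of the second limb on such an event lowers the related count and none raises it. A site that follows one section will code the same event differently from a site that follows the other.

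**Step 3. What is the study drug?** Section 11.3.1.4 does not say. SAP Section 3.1.2 uses the term for etoposide, carboplatin or trilaciclib.

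| Reading | What counts as another drug |
|---|---|
| G1T28 or placebo only | Etoposide and carboplatin |
| Each drug rated separately | For each drug, the other two |
| The combination as one | Only drugs outside the regimen |

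Disease and circumstance remain available as other causes under every reading. The second reading is the one that the SAP outputs need.

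**Step 4. Follow it into the outputs.**

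- *Related AEs and SAEs:* these rest directly on the rating. Keeping the strongest relationship across repeat events (Protocol 13.5.2, SAP 6.2.8.1) helps only if at least one occurrence was rated related.
- *Part 2 comparison:* if a share m of related events is lost equally in both blinded arms, the event counts become (1 − m) × G1T28 count and (1 − m) × placebo count. The ratio is unchanged and the difference shrinks by the factor (1 − m).
- *Part 1:* there is no control arm, so nothing in the data replaces attribution.
- *MAHE component 3:* a death is lost only if the second limb is applied to all three drugs, or if disease or circumstance is taken as the cause.
- *All-cause TEAEs, SAEs and AEs leading to death:* no dependence on the rating.

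**Step 5. DLTs, only if the scale were applied to them.** The plan acts when "At any time, if ≥ 2 DLTs are observed in any given cohort", and cohorts have 6 patients. Let p be the true DLT rate and m the share rated *Unrelated*. Both are assumptions. With q = p(1 − m), the chance of two or more counted DLTs is 1 − (1 − q)^6 − 6q(1 − q)^5.

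| p | m = 0 | m = 25% | m = 50% | m = 75% |
|---|---|---|---|---|
| 0.20 | 0.345 | 0.224 | 0.114 | 0.033 |
| 0.33 | 0.642 | 0.460 | 0.259 | 0.082 |
| 0.50 | 0.891 | 0.726 | 0.466 | 0.167 |

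For p = 0.33 and m = 50%, q = 0.165 and the result is 1 − 0.339 − 0.402 = 0.259. The table shows how sensitive a rule based on six patients would be. It does not estimate what happens in this trial.

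**The case against.** The best defence is that the scale permits *Unrelated* and does not compel it. An investigator who thinks the study drug a reasonable cause can always choose *Possibly Related*. The main safety evidence in Part 2 is the randomized, double-blind comparison of all-cause events, which needs no attribution. All SAEs in the reporting period go to the safety team within 24 hours whatever their cause (Section 11.3.1.9), and the reaction definition tied to expedited reporting is the protective one. All of that stands. It limits the consequences but does not remove the overlap or the conflict between the two sections.

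A reader might go further and infer that most AEs plausibly due to G1T28 or chemotherapy will vanish from the DLT, related-AE and related-death counts. The documents do not support this:

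- No figure gives the share of AEs that would be rated *Unrelated*.
- For DLTs, Section 6.1.1.1 does not invoke the scale. Its closing sentence says that toxicities not clearly due to chemotherapy are considered *also*, which suggests that chemotherapy toxicities are already within scope. Four of its five criteria are cytopenia-type events, and excluding those that chemotherapy can cause would nearly empty the list. The SMC also sees all available data (Section 6.1.1.4). A small gap remains, because *drug* in *drug-related* is undefined.
- For deaths, relation to any one of three drugs suffices. MAHE is a time-to-first-event measure that also counts febrile neutropenia, hospitalization for a hematologic event and Grade 4 neutropenia beyond 5 days. A neutropenic death would usually already be an event without any causality rating.

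**Conclusion.** The concern holds as a defect of definition. The terms in Section 11.3.1.4 are not mutually exclusive, the second limb of *Unrelated* conflicts with Section 11.3.1.1, and *study drug* is undefined where the rating is made. The effect falls mainly on the related-AE and related-SAE summaries. Measured against the Section 11.3.1.1 standard, its direction is known (under-counting, with variation between sites) and its size is not. This rests on two premises: that alternative causes are common in patients who all have small cell lung cancer and all receive etoposide and carboplatin, and that at least some investigators apply the limb as written. Effects on DLTs and MAHE component 3 are secondary and limited by the rules set out above. All-cause tables are unaffected. The eCRF is not among the documents, so it cannot be said that separate ratings per drug are not collected.

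**What to change.** Make three changes in Protocol Section 11.3.1.4 and carry them into the eCRF completion guidance:

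1. Define *Unrelated* as no temporal relationship, or no reasonable possibility that the drug caused or contributed to the AE.
2. State that a plausible alternative cause does not by itself make an AE *Unrelated*, and that *Possibly Related* prevails when the drug and another cause are both reasonable.
3. State that the rating is made separately for G1T28 or placebo, etoposide and carboplatin, as the SAP outputs assume.

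Section 6.1.1.1 should also say what *drug-related* refers to and whether it uses this scale.

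The drafting cost is one redefined clause and a few sentences. The main downside is that more AEs will be labelled possibly related, in both arms. There is also a timing cost. SAP Table 9 describes the Part 1 doses in the past tense, so ratings already exist. Either those rated *Unrelated* because of an alternative cause should be queried before unblinding, or the study report should say that two conventions were in use.

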#### 11.3.1.5. Assessment of the Outcome of Adverse Events

The action taken for study drugs (eg, dose increased, dose not changed, dose reduced, dose interrupted, drug withdrawn, not applicable, unknown) will be recorded on the eCRF.

Other actions (eg, none, concomitant medication given, new or prolonged hospitalization, procedural surgery) will also be recorded on the eCRF.

The outcome will be assessed according to the following:

- Fatal
- Not recovered/not resolved
- Recovered/resolved with sequelae
- Recovering/resolving
- Recovered/resolved
- Unknown

#### 11.3.1.6. Method, Frequency, and Time Period for Detecting Adverse Events and Serious Adverse Events

Safety surveillance reporting of AEs commences at the time of informed consent and continues through 30 days after last dose of study drug (eg, the Post-Treatment Visit).

#### 11.3.1.7. Documentation of Adverse Events and Serious Adverse Events

All AEs will be documented in the appropriate section of the eCRF. The CTCAE, Version 4.03 grading scale referenced in [Appendix 1](#) is provided to assist in categorizing and grading AEs. All SAEs (see Section [11.3.1.2](#)) will be additionally documented on the SAE report form. For AEs occurring while the patient is in the clinic setting, ie, before, during, or after study drug administration, the start time and stop time of the AE should be recorded in the source document.

The following will be recorded for each AE in the eCRF:

- A description of the AE in medical terms, not as reported by the patient. Whenever possible, a diagnosis should be given when signs and symptoms are due to common etiology (eg, cough, runny nose, sneezing, sore throat, and head congestion should be reported as “upper respiratory infection”).
- Date of onset (start date)
- Date of recovery (stop date)
- Grade as assessed by the investigator according to the definitions in the AE Grading Scale. If the AE is not specifically listed in [Appendix 1](#), use the following grades:
  - Grade 1 mild
  - Grade 2 moderate
  - Grade 3 severe
  - Grade 4 life-threatening or disabling
  - Grade 5 death

#### 11.3.1.8. Adverse Event Coding

Adverse event verbatim terms provided by the investigator will be coded by G1 Therapeutics or its designee using the latest version of the Medical Dictionary for Regulatory Activities (MedDRA) as specified in the statistical analysis plan (SAP).

#### 11.3.1.9. Reporting of Serious Adverse Events

The reporting period for SAEs begins from the time of informed consent through and including 30 calendar days after the last administration of G1T28 or placebo + E/P therapy. Any SAE that is thought to be related to the study drug and that occurs after the reporting period must be reported **within 24 hours** of discovery of the SAE.

All SAEs must be entered into the eCRF and the initial SAE form should be completed and sent to the safety team within 24 hours of first knowledge of the event by the study personnel. The contact information for the safety team will be provided in the Site Reference Manual.

In addition, any known untoward event that occurs subsequent to the AE-reporting period that the investigator assesses as related to the investigational medication should also be reported as an AE.

